### Statistical Pre-analysis:

The sample size was calculated using the online calculator at [www.sealedenvelope.com](http://www.sealedenvelope.com). Assuming a power of 90% and an error margin of 5%, the required number for each group (experimental and control teeth) was found to be 43. Since a split-mouth design will be used, in which each patient will have both experimental and control groups, the required number of participants was also determined to be at least 43. Considering possible dropouts during the study, the final sample size was set at 50 participants. Randomization will be achieved using a blocked randomization technique at [www.sealedenvelope.com](http://www.sealedenvelope.com). For blocked randomization, the seed number will be set as 12345 and block size as 2.

In the second phase, volunteer participants will be selected among patients who apply to the Faculty of Dentistry, Başkent University, and are referred to the Department of Restorative Dentistry for treatment after clinical and radiological examination revealed carious lesions. The inclusion criteria will be as follows:

- Voluntary acceptance of participation in the study
- Age between 18–65 years
- Presence of at least 12 teeth in occlusion
- The teeth to be included must have natural antagonists and adjacent teeth (normal occlusion)
- Anterior or posterior teeth with primary or secondary carious lesions in which the cavity preparation is expected to approach the pulp closely but without pulpal exposure
- Each participant must have two teeth, one on the right and one on the left, fulfilling the above criteria
- Absence of any other factor causing sensitivity or pain that might interfere with evaluation

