## STATISTICAL ANALYSIS

Measurements will be obtained from two paired teeth of the same patient. The VAS and NRS values of these paired groups will be compared. For this purpose, chi-square test will be used for NRS values, and independent two-sample t-test will be used for VAS values. The significance level will be set at  $p = 0.05$ .

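### The two teeth of a pair may differ in position and lesion type, and the analysis uses neither these features nor the pairing, which costs precision but causes no bias

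*Combined protocol and SAP*

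**What the plan says.** The inclusion criteria, under Statistical Pre-analysis, admit "Anterior or posterior teeth with primary or secondary carious lesions", provided that the prepared cavity should come near the pulp and not expose it. The pairing rule is "Each participant must have two teeth, one on the right and one on the left, fulfilling the above criteria". No section requires the two teeth to match in position, arch, lesion type or cavity class. The restoration procedure in Materials and Methods expects cavity type to vary, since the matrix system is chosen by it. Which of the two cavities receives the desensitizer is decided at random.

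The sample size paragraph sets 90% power and a 5% error level and reports that "the required number for each group (experimental and control teeth) was found to be 43". That number is carried over to participants because of the split-mouth design, and "the final sample size was set at 50 participants" to allow for dropout.

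The Statistical Analysis section recognises the pairs ("The VAS and NRS values of these paired groups will be compared"). It nevertheless names a chi-square test for the NRS and an independent two-sample t-test for the VAS, and it mentions no pair term, covariate or stratification.

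**The concern.** A split-mouth design gains precision to the extent that the two teeth of a patient would score alike if treated alike. Any difference between them that is unrelated to treatment enters the within-patient difference and widens its confidence interval. Under the current criteria, an anterior tooth with a primary lesion may be paired with a posterior tooth with a secondary lesion. If position or lesion type affects postoperative sensitivity, such pairs add variance that a model could partly remove. The planned tests cannot do so: they have no place for these features and they also discard the pairing. At stake is the width of the interval for the treatment effect.

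**Working it through.** **The plan's own figure.** The documents give no effect size, SD, event rates or within-patient correlation, so 43 cannot be reproduced from stated inputs. It can be back-solved. For independent groups at two-sided 5% (sidedness is not stated) and 90% power:

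- n per group = 2 × (1.960 + 1.282)² / d² = 2 × 10.51 / d².
- n = 43 gives d = 0.699. Put in as d = 0.70, the formula gives 42.9, rounded up to 43.

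The stated number therefore fits an independent-groups calculation at 0.70 SD, with no credit taken for pairing. This is an inference.

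**Effect of unlike teeth on a paired comparison.** Assumed inputs, none of them in the documents:

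- r, the correlation between two teeth of the same type in one patient: 0.5, with 0.7 as a variant.
- m, the share of discordant pairs: 0.2 or 0.4.
- δ, the tooth-type effect in SD units: 0.2, 0.5 or 0.8.

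Random allocation makes the sign of the tooth-type difference random, so it adds mδ² to the variance:

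Var(difference) = 2(1 − r) + mδ²

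At r = 0.5 the first term is 1, so mδ² is itself the proportional rise. The last column is 43 / (1 + mδ²).

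| δ | m | mδ² | Rise in variance | 43 pairs equivalent to |
|---|---|---|---|---|
| 0.2 | 0.2 | 0.008 | 0.8% | 42.7 |
| 0.2 | 0.4 | 0.016 | 1.6% | 42.3 |
| 0.5 | 0.2 | 0.050 | 5.0% | 41.0 |
| 0.5 | 0.4 | 0.100 | 10.0% | 39.1 |
| 0.8 | 0.2 | 0.128 | 12.8% | 38.1 |
| 0.8 | 0.4 | 0.256 | 25.6% | 34.2 |

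In the last row the confidence interval widens by √1.256 = 1.12, or 12%. At r = 0.7 the first term is 0.6. With m = 0.4 the rise is then 0.016/0.6 = 2.7%, 0.100/0.6 = 16.7% and 0.256/0.6 = 42.7% for the three values of δ.

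**Comparison with the planned size.** An independent-groups calculation assumes a variance of 2 for the difference between two teeth. The worst cases above are 1.256 (r = 0.5) and 0.6 + 0.256 = 0.856 (r = 0.7). At d = 0.70, a paired analysis would need 1.256 × 10.51 / 0.49 = 26.9, so 27 pairs, or 0.856 × 10.51 / 0.49 = 18.4, so 19 pairs. The plan has 43.

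**Loss from ignoring the pairing.** At r = 0.5 the independent t-test works with a variance of 2 where the paired variance is 1, so its interval is wider by √2 = 1.41, or 41%. Its actual two-sided alpha is about 0.0056. With 43 pairs and d = 0.70, its power is 96.5%, against 99.6% for a paired test. At a correlation of 0.3 the alpha is about 0.019 and the power 93.8%, against 97.3%.

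**Net gain from the covariates.** In simulation with 43 pairs, fitting two within-pair contrasts that have no effect costs about 5% of precision. At r = 0.5 the net variance ratio, unadjusted to adjusted, is roughly:

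- 1.008 / 1.05 = 0.96 (a small loss) at δ = 0.2, m = 0.2;
- 1.05 / 1.05 = 1.00 (break-even) at δ = 0.5, m = 0.2;
- 1.256 / 1.05 = 1.20 (a gain) at δ = 0.8, m = 0.4.

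**The case against.** The strongest objection is that the documents never link tooth position or lesion type to sensitivity. The Introduction names remaining dentin thickness, tubule diameter and patency, pulp condition and clinician factors. The plan already narrows several of these: both cavities must be expected to come close to the pulp, non-vital teeth are excluded, and one operator uses the same materials throughout. This stands. A reader might infer from the Introduction that unlike teeth are known to differ in expected score, but that step is an assumption. Position and lesion type are at best proxies for the named causes.

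A reader might also infer three stronger conclusions that the documents do not support.

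- **Bias.** The treated tooth is chosen at random within the pair, so unlike teeth do not favour either arm systematically. A chance imbalance in one trial is the same random error as the mδ² term and is not a second harm.
- **Too few patients.** Describing 43 pairs as equivalent to 34 suggests a shortfall. The stated number appears to take no credit for pairing, and even the worst cases above stay well below the variance it seems to assume.
- **Unlike teeth as the main loss.** On the figures above, most of the recoverable precision comes from pairing the analysis (41% in interval width at r = 0.5, against at most 12% from tooth type). Using unpaired tests on paired data is the larger defect, and the covariates are an increment to its correction.

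Finally, eligibility does not turn on either classification, and no section says that lesion type is recorded. Position is evident for any tooth, but lesion type would need a line on the case form.

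**Conclusion.** The point holds as a minor one about efficiency. The criteria allow unlike teeth within a pair, and the named tests use neither the pairing nor the features that make the teeth unlike. If those features affect sensitivity, the consequence is a wider confidence interval than necessary. The rise of about 1 to 26% in the variance of the paired difference rests wholly on assumed values (correlation 0.5, discordance 20 to 40%, tooth-type effect 0.2 to 0.8 SD) and would be larger at a higher correlation. If the tooth-type effect is near 0.2 SD, adjustment returns nothing or costs slightly. The change is still worthwhile because the paired model is needed in any case and the two covariates cost little.

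**What to change.** Leave eligibility as it is. In the Statistical Analysis section:

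1. Replace the independent t-test for the VAS with a paired analysis in which treatment is the effect of interest. This can be a mixed model with patient as a random effect, or a regression of the within-patient difference on the within-pair covariate contrasts, with the intercept as the treatment effect. Name one of the two.
2. Record tooth position (anterior or posterior) and lesion type (primary or secondary) for each tooth, and prespecify both as tooth-level covariates before outcome data are seen.
3. Replace the chi-square test for the 0 to 4 NRS with a paired ordinal counterpart.
4. Report the unadjusted paired result as a sensitivity analysis.

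The change needs SAP wording and two recorded items, with no extra patients, visits or procedures. It uses two degrees of freedom and loses about 5% of precision if neither covariate is prognostic. In the regression of differences, the covariate effects rest on the discordant pairs alone. At 20% discordance that is about 9 of 43 (0.2 × 43 = 8.6), so those effects should not be interpreted in their own right.

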### INTRODUCTION AND GENERAL INFORMATION

Nowadays, both esthetic concerns and ecological awareness have led to the preference of composite resin instead of amalgam in most restorations. However, the acidic adhesive monomers used during the application of composite resins can cause pain following restoration. This type of pain, defined as postoperative sensitivity, generally occurs independently of restoration failure and is reported by patients at different levels and intensities. Typically, this pain lasts for a period of several days to one month after the restoration and then subsides. In rare cases where severe pain occurs, endodontic treatment may become necessary (1).

Postoperative sensitivity may arise due to several factors, including the remaining dentin thickness, the diameter and patency of dentin tubules after acid etching, the general condition of the pulp, and clinician-related factors (2). To reduce postoperative sensitivity, several approaches have been suggested, such as avoiding excessive drying during cavity preparation (3), applying desensitizers and liners to the cavity (2), and using self-etch adhesives (4). However, current evidence shows that the type of adhesive itself is not a determining factor for postoperative sensitivity (5). It has also been reported that desensitizers applied to the cavity may influence bond strength. Therefore, careful selection of the material to be applied is important for the success of the restoration.

Teethmate Desensitizer (Kuraray Noritake), a desensitizing agent containing tetracalcium phosphate and dicalcium phosphate anhydrous, forms hydroxyapatite through a dissolution-precipitation reaction. An in vitro study demonstrated that this material does not adversely affect bond strength (6). Another in vitro study (7) reported that while Teethmate Desensitizer reduced adhesive bond strength, it also decreased microleakage. For this reason, it was suggested that in multimode adhesives used in self-etch mode, Teethmate Desensitizer could be applied to the cavity before adhesive application in order to reduce postoperative sensitivity.

Although the effectiveness of Teethmate Desensitizer in occluding dentin tubules and reducing sensitivity has been reported in clinical studies (8–10), no study investigating its effect on postoperative sensitivity following composite resin restorations has been identified.

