### Exclusion criteria:

- Refusal to participate in the study
- Age under 18 or over 65 years
- Presence of dental or orofacial pain
- Presence of bruxism
- Presence of advanced periodontal disease
- Presence of systemic diseases that may hinder treatment procedures or follow-up visits
- Teeth with excessive loss of tooth structure requiring full crown restoration, or with severe attrition, cracks, or non-vital teeth
- Pulpal exposure during cavity preparation
- Presence of gingival recession
- Use of analgesics, anti-inflammatory, or psychotropic drugs within the last 15 days or currently using them
- Pregnancy or lactation
- Known allergy to the materials to be used

Eligible individuals will be invited to participate in the study after verbal explanation

of the purpose and methodology. Participation will be voluntary, and those who accept will sign an Informed Consent Form. If deemed necessary, participants will receive oral hygiene motivation, and interventions will begin once oral hygiene has reached a satisfactory level.

In the third phase, before starting treatment of the teeth diagnosed with caries through clinical and radiological examination, vitality tests will be performed. After cavity preparation of two teeth per participant, the cavities will be isolated. At the point closest to the pulp, a calcium hydroxide-based pulp capping agent (Dycal, Dentsply Sirona, York, USA) will be applied in paste form. Subsequently, Teethmate Desensitizer will be applied according to the manufacturer's instructions to one cavity randomly, while the other will receive no desensitizer. To ensure randomization, pre-prepared allocation lists from [www.sealedenvelope.com](http://www.sealedenvelope.com) will be placed in opaque envelopes, which will be opened only at the time of intervention.

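### Achieved cavity depth is never recorded, so depth differences between a patient's two teeth cannot be adjusted for and the depth studied cannot be reported

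*Combined protocol and SAP*

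**What the plan says.** Under Statistical Pre-analysis, the depth criterion is a forecast: an eligible tooth is one where "the cavity preparation is expected to approach the pulp closely but without pulpal exposure". No depth or dentin-thickness threshold is attached. Each participant contributes one right and one left tooth. These may be anterior or posterior, with primary or secondary caries, and nothing requires the two to match.

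The list under Exclusion criteria contains one rule that depends on the depth actually found: "Pulpal exposure during cavity preparation". The third-phase text below it then sets the order of work: "After cavity preparation of two teeth per participant, the cavities will be isolated". A liner follows ("At the point closest to the pulp, a calcium hydroxide-based pulp capping agent"), and then one cavity receives the desensitizer at random, from "opaque envelopes, which will be opened only at the time of intervention". No step measures, grades or records depth.

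The Introduction states: "Postoperative sensitivity may arise due to several factors, including the remaining dentin thickness". The Statistical Analysis section plans a chi-square test for NRS and an independent two-sample t-test for VAS, both unadjusted.

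**The concern.** Depth defines the eligible tooth, and the plan itself treats the dentin left over the pulp as relevant to the outcome. But depth is known to the trial only as a prediction made before drilling. Once both cavities are open the true depth is in view, and it is not written down.

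Two things are at stake. First, a split-mouth design gains precision by comparing like with like within a patient. If one cavity of a pair is deep and the other is not, and depth affects pain, the pair's VAS difference carries a depth component on top of the treatment effect. Unrecorded, that component stays in the error. Second, after a null result nobody could tell whether the agent failed or whether many cavities were too shallow to become sensitive. The report could give only the intended depth, not the depth achieved.

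**Working it through.** **The plan's own figure.** Statistical Pre-analysis gives 43 per group ("Assuming a power of 90% and an error margin of 5"%) and 50 participants after an allowance for dropout. No effect size, SD or event rate is stated, so 43 can only be back-solved. Taking the 5% as two-sided (the plan does not say), 1.960 + 1.2816 = 3.2415, and:

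- independent groups: standardised difference = √2 × 3.2415 / √43 = 0.699
- paired differences: 3.2415 / √43 = 0.494
- step to 50: 1 − 43/50 = 14% implied loss

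Nothing in these figures refers to depth.

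**Noise within pairs.** For patient i let D be VAS in the treated tooth minus VAS in the control tooth, and G the depth grade of the treated tooth minus that of the control tooth. Unadjusted, the treatment effect is the mean of D. Adjusted, it is the intercept β₀ in D = β₀ + β₁G + error. If ρ is the correlation between D and G, the residual variance is about (1 − ρ²) times the unadjusted variance. The price with 43 pairs is one degree of freedom (43 − 1 = 42 becomes 41). The documents give no value for ρ, so the gain cannot be sized. It is zero if pairs happen to match on depth.

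**Direction of error.** The desensitizer is assigned at random within the patient after both cavities are prepared, so G has expectation zero. The unadjusted comparison is noisier but not biased.

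**Illustration of dilution.** Let f be the share of shallow cavities and r the effect in them relative to deep ones (both assumed), with the SD held fixed. The mean difference is multiplied by k = 1 − f(1 − r), and power at 43 is Φ(3.2415k − 1.960).

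| f | r | k | Power |
|---|---|---|---|
| 0 | – | 1.00 | 90% |
| 10% | 0 | 0.90 | 83% |
| 20% | 0 | 0.80 | 74% |
| 10% | 0.5 | 0.95 | 87% |
| 20% | 0.5 | 0.90 | 83% |

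**Would dropping shallow pairs help?** If the two teeth are independent, both are deep in (1 − f)² of pairs: 81% at f = 10% and 64% at f = 20%, which is 34.8 and 27.5 of 43. With the full effect in those pairs, power is Φ(3.2415 × √0.81 − 1.960) = 83% and Φ(3.2415 × √0.64 − 1.960) = 74%. That equals the all-pairs power at r = 0 and falls below it at r = 0.5. Exclusion without replacement therefore gains no power even in the worst case shown. With replacement, 50 pairs need 50/0.81 ≈ 62 or 50/0.64 ≈ 78 prepared patients.

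**The case against.** The strongest reply is that choosing teeth by pre-operative clinical and radiological judgement is a legitimate design. The stated aim concerns composite restorations generally, not confirmed-deep cavities only. The Introduction lists remaining dentin thickness as one factor among several, without ranking them, and nowhere says that shallower cavities hurt less or respond less to the agent. All of this stands, and it limits the point to precision and reporting.

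A reader might infer three stronger things.

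- **The contrast is diluted and the trial underpowered.** The documents do not support this as a finding. The shallow share, the missing effect in shallow teeth and the fixed SD are all assumptions. If the unstated planning effect came from cavities of mixed depth, dilution is already built in.
- **Removing exposures but not shallow cavities biases the comparison.** It does not, because exposure is found during preparation, before allocation is known.
- **Exposures will use up the 7-pair margin.** With exposure probability p per tooth, 50(1 − p)² leaves 45.1 pairs at 5%, 43.0 at about 7.3% and 40.5 at 10%. Those rates have no source in the documents, the formula treats a patient's two teeth as independent, and the 50 can be read as patients who pass the exclusions. Because consent precedes preparation, the wording is ambiguous, but a clarification is enough.

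A further objection concerns the obvious remedy, excluding shallow cavities after drilling. On the assumed 10% or 20%, it would reject 19% or 36% of pairs. It would also give the single operator a subjective choice just before an envelope drawn from blocks of 2 with a published seed, where the second allocation in each block follows from the first. That objection stands, and the fix avoids the step.

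**Conclusion.** The point holds as a gap in recording and analysis. Depth defines eligibility and is named as relevant to the outcome, but achieved depth is neither captured nor used. The consequences are a possible loss of precision from depth differences within pairs and a report that cannot describe the cavities studied. There is no bias between arms.

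The size is unknown. Precision is gained only if depth affects VAS and differs within pairs. The power range of 74% to 87% illustrates what shallow cavities could do under stated assumptions. It is not an estimate for this trial, and recording depth would not by itself restore power lost that way. This is a cheap improvement worth making, not a flaw that undermines the design.

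**What to change.** **Third-phase text under Exclusion criteria.** State that after both cavities are prepared, and before the envelope is opened, the operator records a depth grade for each tooth on a scale defined in advance. Recording before opening keeps the grade independent of allocation. Do not add a discretionary exclusion of shallow cavities.

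**Statistical Analysis.** Make the VAS comparison within patient and adjust it for the within-pair difference in depth grade, as in the model above. Add a sensitivity analysis in pairs where both cavities were graded deep. The grade is fixed before allocation, so that subset remains a randomised comparison, though a smaller one. Report the distribution of grades by arm.

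**Statistical Pre-analysis.** As a clarification, state that the 50 participants are counted at envelope opening, so that patients excluded for exposure are not among them.

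**Cost.** One extra field per tooth at a step already performed, and a slightly more complex model than the planned unadjusted tests. The grade remains an operator's judgement, so its definition should be fixed before the first patient.

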### Exclusion criteria:

- Refusal to participate in the study
- Age under 18 or over 65 years
- Presence of dental or orofacial pain
- Presence of bruxism
- Presence of advanced periodontal disease
- Presence of systemic diseases that may hinder treatment procedures or follow-up visits
- Teeth with excessive loss of tooth structure requiring full crown restoration, or with severe attrition, cracks, or non-vital teeth
- Pulpal exposure during cavity preparation
- Presence of gingival recession
- Use of analgesics, anti-inflammatory, or psychotropic drugs within the last 15 days or currently using them
- Pregnancy or lactation
- Known allergy to the materials to be used

Eligible individuals will be invited to participate in the study after verbal explanation

of the purpose and methodology. Participation will be voluntary, and those who accept will sign an Informed Consent Form. If deemed necessary, participants will receive oral hygiene motivation, and interventions will begin once oral hygiene has reached a satisfactory level.

In the third phase, before starting treatment of the teeth diagnosed with caries through clinical and radiological examination, vitality tests will be performed. After cavity preparation of two teeth per participant, the cavities will be isolated. At the point closest to the pulp, a calcium hydroxide-based pulp capping agent (Dycal, Dentsply Sirona, York, USA) will be applied in paste form. Subsequently, Teethmate Desensitizer will be applied according to the manufacturer's instructions to one cavity randomly, while the other will receive no desensitizer. To ensure randomization, pre-prepared allocation lists from [www.sealedenvelope.com](http://www.sealedenvelope.com) will be placed in opaque envelopes, which will be opened only at the time of intervention.

When necessary depending on cavity type, a matrix system (Mylar strip, sectional matrix, or Tofflemire) will be applied before restoration. All cavities will be treated with a one-step self-etch adhesive (Clearfil SE Bond, Kuraray Noritake, Tokyo, Japan) according to manufacturer's instructions and light-cured with an LED unit (LedMax Cordless 550, Benlioğlu Dental, Ankara, Turkey) at a constant intensity  $>1,500$  mW/cm^2 for 10 seconds. Restorations will be completed using a universal composite resin (Filtek Z250, 3M Espe, St. Paul, MN, USA) with the oblique incremental technique. Each increment of composite will be polymerized for 20 seconds with the same LED device. Finishing and polishing will be performed using diamond finishing burs, polishing rubbers, and disks (Soflex, 3M Espe, St. Paul, MN, USA). All restorations will be performed by a single operator.

After restoration, participants will be given two forms (one for each tooth) to record their daily pain levels for one week. Instructions for filling out the forms will be provided. The forms will include the Numerical Rating Scale (NRS, 0–4) and the Visual Analog Scale (VAS, 0–100 mm). One week later, patients will return for follow-up, and the completed forms will be collected. Six weeks after the restorations, patients will return for another follow-up. At both the one-week and six-week follow-up visits, restorations will be evaluated by another dentist to ensure double blinding.

At the one-month control visit, tooth vitality will first be assessed. If the tooth is vital, postoperative sensitivity will be evaluated using VAS scores and by applying a cold spray (Ice Spray, Picdare S.p.A, Casnate con Bernate, Italy) with a cotton pellet to the mid-buccal surface of the teeth for 5 seconds.

Study Start Date: May 3, 2021

Study Completion Date: May 3, 2022

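### The late cold-stimulus VAS has no scored pre-treatment counterpart; a baseline cold VAS used as a covariate would be a cheap gain in precision, not a correction of bias

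*Combined protocol and SAP*

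**What the plan says.** All references are to the combined protocol and SAP.

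- **Before treatment** (Materials and Methods, third-phase paragraph after the exclusion criteria): "vitality tests will be performed". No method, score or record is described.
- **First scored pain** (Materials and Methods, paragraph after the restoration procedure): "After restoration, participants will be given two forms (one for each tooth) to record their daily pain levels for one week". Scoring therefore begins only once both teeth are restored.
- **Late visit**: "At the one-month control visit, tooth vitality will first be assessed". For a vital tooth, "postoperative sensitivity will be evaluated using VAS scores and by applying a cold spray" "with a cotton pellet to the mid-buccal surface of the teeth for 5 seconds". I read this as a VAS marked in response to the cold stimulus, although the sentence does not quite say so. The paragraph before it schedules the second follow-up at six weeks, not one month.
- **Pairing** (inclusion criteria, under Statistical Pre-analysis): each patient contributes one tooth from each side. Either tooth may be anterior or posterior, and the caries may be primary or secondary. Nothing requires the two to match.
- **Allocation**: one of the two cavities is chosen at random to receive the desensitizer.
- **Analysis** (Statistical Analysis): "The VAS and NRS values of these paired groups will be compared". VAS is compared by an unpaired t-test with no baseline term.

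**The concern.** A vital tooth can respond to cold whatever was placed in the cavity. The late VAS therefore contains each tooth's ordinary responsiveness as well as any postoperative component. Using the patient as his or her own control removes differences between patients but not differences between the two teeth of a patient. Since an anterior tooth with a primary lesion may be paired with a posterior tooth with a secondary one, those differences could be appreciable. Excluding patients with dental pain or other causes of sensitivity screens out complaints; it does not measure or equalise the response to a provoked stimulus.

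At stake are the precision of the late cold comparison and the ability to correct a chance imbalance between unmatched teeth. A pre-treatment response cannot be recovered once the teeth have been restored.

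**Working it through.** **The plan's own figure.** Statistical Pre-analysis gives 43 teeth per group, hence 43 patients, raised to 50 for dropout: "Assuming a power of 90% and an error margin of 5"%. It states no effect size, SD, outcome or test, so 43 cannot be reproduced. It is consistent with, for example, an unpaired two-sided comparison at an assumed standardised difference of 0.70: 2 × (1.960 + 1.282)² / 0.70² ≈ 42.9, rounded up to 43. Other inputs also give 43. I use 43 only as a number of pairs.

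**Is the comparison biased without a baseline?** No. The treated tooth is randomised, so a pre-existing difference falls on either arm by chance. A simulation of 20,000 trials of 43 pairs at ρ = 0.3, 0.5 and 0.7 gave a mean bias of about 0 and type I error of 4.9% to 5.1% for an unadjusted paired test.

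**How much precision would a baseline add?** Let D be the late VAS difference (treated minus control), B the same difference before treatment, and ρ their correlation. The documents do not give ρ; 0 to 0.6 is an assumed range.

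- Regressing D on B multiplies the variance of the treatment effect (the intercept) by 1 − ρ².
- Estimating the slope multiplies it, under normality, by about 1 + 1/(n − 3) = 1 + 1/40 = 1.025.
- Effective pairs = 43 / [1.025 × (1 − ρ²)].
- Using the change score D − B instead multiplies the variance by 2(1 − ρ), if B and D have equal variance.

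| Assumed ρ | 1 − ρ² | × 1.025 | 43 pairs worth about | Change in SE | Change-score factor |
|---|---|---|---|---|---|
| 0 | 1.00 | 1.025 | 42 | +1.2% | 2.0 |
| 0.2 | 0.96 | 0.984 | 44 | −0.8% | 1.6 |
| 0.3 | 0.91 | 0.933 | 46 | −3.4% | 1.4 |
| 0.4 | 0.84 | 0.861 | 50 | −7.2% | 1.2 |
| 0.5 | 0.75 | 0.769 | 56 | −12.3% | 1.0 |
| 0.6 | 0.64 | 0.656 | 66 | −19.0% | 0.8 |

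**Break-even.** 1 − ρ² = 1/1.025 = 0.976, so ρ² = 0.024 and ρ ≈ 0.16.

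**Check.** The simulated SE fell from 0.1520 to 0.1474 at ρ = 0.3 (3%) and from 0.1528 to 0.1338 at ρ = 0.5 (12%), in line with the table.

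**Change score.** Its factor is above 1 whenever ρ is below 0.5. At ρ = 0.3 it would take 43 × 1.4 = 60.2, that is 61 pairs, to match 43 pairs analysed with no baseline at all.

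**The case against.** A reader might infer that a tooth which was always cold-sensitive is wrongly counted against a treatment, so that the comparison is confounded. The documents do not support that. The tooth is allocated at random, and the stated aim is a comparison with control, not an absolute level of sensitivity in either arm.

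The rest of the case against has substance:

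- **The correlation may be low.** The baseline would be taken on an untreated carious tooth whose cavity is expected to come close to the pulp. The late value follows caries removal, liner, adhesive and composite, so the source of much of the early response may be gone. At ρ = 0.2 the gain is about one pair. This stands, and is why the range runs down to 0.
- **The reference is not the planned analysis.** The figures compare an adjusted with an unadjusted paired analysis, whereas the plan has an unpaired t-test. That is a separate loss and may be the larger one. At the assumed 0.70, a paired analysis would need about 31, 22 or 13 pairs rather than 43 if the two teeth correlate at 0.3, 0.5 or 0.7. This stands; both changes belong in one edit.
- **Only one outcome benefits.** A cold baseline is not the natural baseline for the week-one daily forms. The Introduction also says this pain usually subsides within a month, so the late test may not carry the main signal, and no primary outcome is named. This stands.
- **The test may not already be in the plan.** The late-visit text treats vitality and cold spray as separate steps and the pre-treatment method is unspecified, so a cold test might have to be added. This stands as a small cost.
- **Eligibility narrows the variation.** Excluding pain, recession, cracks, severe attrition and recent analgesic use helps, but it does not equalise cold response.

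**Conclusion.** The point holds as a cheap improvement limited to the late cold-stimulus VAS. The plan keeps no scored pre-treatment cold response, and the pairs are not matched on tooth position or lesion type. The treatment comparison is nevertheless valid without a baseline.

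The possible gain runs from nothing (ρ below about 0.16) through about 3 pairs (ρ = 0.3) to 13 pairs (ρ = 0.5) or 23 pairs (ρ = 0.6) on top of 43. Nothing in the documents says where in that range the trial lies.

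These figures assume that randomisation is carried out as described, that 43 patients have both teeth evaluated at the late visit, that the VAS differences are roughly normal, and that the comparator is a paired analysis. The 43 is not tied to this outcome, so I do not translate the gain into power.

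**What to change.** 1. **Materials and Methods, third-phase paragraph.** Before treatment, have the patient mark a VAS for each tooth in response to the same cold spray, pellet, site and 5-second application as at the late visit. State explicitly that the late VAS is marked in response to that stimulus.
2. **Statistical Analysis.** For the late cold VAS, replace the unpaired t-test with a regression of the within-patient late difference (treated minus control) on the within-patient baseline difference. The intercept is the treatment effect. A mixed model is acceptable if it also includes the patient-mean baseline, or uses fixed patient effects. A random-intercept model with raw baseline VAS alone is not equivalent, because its slope blends between-patient and within-patient associations. Do not use a simple change score.
3. **Late visit.** Reconcile the one-month and six-week labels, so that it is clear when the cold VAS is taken.

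Cost: two VAS marks per patient, one covariate, and possibly one brief, non-invasive cold test per tooth if the current vitality test uses another method. No extra visit or staff is needed. If ρ proves close to zero, the adjustment costs about one pair's worth of information.
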